#### **Discharge Form**

A Discharge Form should be completed for all randomised patients on discharge from the randomising centre or in the event of earlier death. This form should be returned to the CLOTS Co-ordinating Centre in Edinburgh. The data collected includes:

- Use of thrombolysis, heparin, warfarin and antiplatelet drugs during admission
- Compliance with treatment allocation (including the use of full length or below knee stockings)
- Any clinical DVT or PE requiring treatment (diagnosis will be reviewed blind to the treatment allocation) or any further vascular event during admission.
- Any complications of treatments
- Contact details to facilitate 6 month follow up

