#### Antithrombotic Drugs to Prevent Post Stroke DVT

Both low and medium dose subcutaneous heparin reduce the risk of DVT, and probably PE, in patients with acute ischaemic stroke (Gubitz et al 2000). However, evidence from the International Stroke Trial (IST 1997) shows that even low dose heparin (5,000 unit twice daily) is associated with a significant excess of symptomatic intracranial and extracranial bleeds which offset any other advantages heparin may have on recurrent ischaemic stroke and fatal PE. Trials have demonstrated that aspirin is probably effective in preventing DVT and PE after surgery (The Antiplatelet Trialists' Collaboration 1994, Pulmonary Embolus Prevention Trial 1999). The results of the IST and the Chinese Acute Stroke Trial (CAST) suggest that aspirin should be started in all patients with a proven ischaemic stroke as soon as possible since it is associated with a reduced risk of death and recurrence within the first month (Gubitz et al 2000). Therefore all patients with stroke, except those with haemorrhagic stroke or with other contraindications to aspirin, should be treated with aspirin. This might also be expected to reduce the frequency of DVT and PE. Indeed in the IST, although DVT was not an endpoint, aspirin was associated with a reduction in risk of PE in the first two weeks from 0.8% to 0.6% (2p = 0.08, odds reduction 26% (95% CI 48% reduction to 4% increase) IST 1997).

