**Doppler ultrasound** imaging provides a very accurate and specific tool to detect above knee thrombus in symptomatic patients. There is more uncertainty concerning its sensitivity and specificity for detecting calf vein thrombus and in asymptomatic patients (Davidson 1998). Reported sensitivities in asymptomatic patients vary between 42% and 70% with positive predictive values varying between 35% and 83% depending on the operator's expertise and the prevalence of DVT in the patient group examined. However, it is rapidly becoming the investigation of choice to confirm the diagnosis of DVT since it is non invasive (Baxter 1997). It is acceptable to patients, can easily be repeated several times and uses equipment which is widely available. Thus consent, accrual and compliance in a trial are likely to be more easily achieved than with alternatives.

**Plethysmography** This technique is of comparable accuracy to Doppler ultrasound and is also non invasive but it is not widely available in centres which are likely to participate in this randomised trial.

**Magnetic Resonance Imaging** Preliminary reports suggest that this technique might offer an alternative non invasive method of detection. However it is available in very few centres and has not yet been fully evaluated (Moody 1997, Kelly et al 2001).

**D-Dimers** are degradation products produced when thrombus present in the circulation is lysed. Raised levels of D-Dimers have been used as a very sensitive but less specific test for diagnosis of DVT (Bounameaux et al 1997). However, its performance in detecting DVT/PE in prevention studies remains to be established. At this time it could not be used as a test to confirm DVT, but given its sensitivity it might be used as a preliminary screening test to select patients for imaging (Harvey et al 1996, Bernardi et al 1998)

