#### Management of DVT in the Trial

A Radiology Report Form should be completed for all Doppler ultrasounds and venograms. This form, and in the case where there is evidence of DVT, the best image, still or video, should be returned to the CLOTS Co-ordinating Centre in Edinburgh.

If a popliteal or femoral vein DVT is detected during the routine Doppler ultrasound examinations, the responsible clinician will need to decide whether to confirm the presence and extent of any thrombus using venography. Although they may only perform confirmatory venography where the Doppler ultrasound is equivocal in their normal practice, compared with treating patients with a swollen leg the positive predictive value of a screening Doppler ultrasound study performed in an asymptomatic patient is likely to be lower. Put another way, the Doppler result is more likely to produce a false positive result in an asymptomatic patient. If the clinician is satisfied that the patients has a DVT (with or without a confirmatory venogram) the patient should be anticoagulated using subcutaneous heparin according to local protocols as long as there is no contraindication (SIGN Guidelines 1999).

If only calf vein thrombus is detected (by screening Doppler ultrasound and/or venography), the responsible clinician may anticoagulate the patient according to local protocols or alternatively arrange a follow up Doppler ultrasound approximately seven days later to identify any propogation into the popliteal vein. If definite popliteal or femoral vein thrombus is detected the patient should be anticoagulated unless contraindicated. If calf vein thrombus is detected during the first scheduled scan (between Day 7 to 10) a scan should also be performed between Days 25 and 30 in addition to any other scans deemed necessary.

If a patient develops symptoms or signs suggestive of DVT during their admission they should be investigated by either Doppler ultrasound and/ or venography and treated according to local protocols if the diagnosis is confirmed. Such patients should still have a Doppler ultrasound between Day 25 and 30 blinded to treatment allocation.

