During the period of recruitment into the study, interim analyses of in-hospital mortality and of any other information that is available on major outcome events (including serious adverse events believed to be due to treatment) will be supplied, in strict confidence, to the chairman of the data monitoring committee, along with any other analyses that the committee may request. In the light of these analyses, the data monitoring committee will advise the chairman of the steering committee if, in their view, the randomised comparisons in CLOTS have provided **both** (i)"proof beyond reasonable doubt" that for all, or for some, specific types of patient, one particular treatment is clearly indicated or clearly contraindicated in terms of a net difference in mortality or serious morbidity, **and** (ii) evidence that might reasonably be expected to influence materially the patient management of the many clinicians who are already aware of the results of the other main trials. The steering committee can then decide whether to modify intake to the study (or to seek extra data). Unless this happens, however, the steering committee, the collaborators, and the central administrative staff (except those who produce the confidential analyses) will remain ignorant of the interim results.

Collaborators, and all others associated with the study, may write through the CLOTS office, Edinburgh to the chairman of the data monitoring committee, drawing attention to any worries they may have about the possibility of particular side-effects, or about particular categories of patient requiring special consideration, or about any other matters that may be relevant.

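### The protocol says the Discharge Form collects further vascular events and treatment complications, but no form has an item for bleeding or for non-fatal vascular events other than DVT and PE

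*Protocol*

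**What the plan says.** The Discharge Form section of the protocol lists what the form collects. Besides drug use, compliance and contact details, the list has clinical DVT or PE needing treatment "or any further vascular event during admission", and, as a separate item, "Any complications of treatments".

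Management of DVT in the Trial says that once the clinician accepts that a popliteal or femoral DVT is present, with or without venography, "the patient should be anticoagulated using subcutaneous heparin according to local protocols as long as there is no contraindication". The background section on antithrombotic drugs says that even low dose heparin, in acute ischaemic stroke, carries a "significant excess of symptomatic intracranial and extracranial bleeds".

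Secondary Outcomes names medical complications of stockings among the in-hospital outcomes. It lists no bleeding outcome and no vascular event other than DVT and PE.

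The data monitoring text (just before Publication of the Trial Results) asks the committee to advise whether a treatment is "clearly indicated or clearly contraindicated in terms of a net difference in mortality or serious morbidity". For this it is to receive in-hospital mortality and whatever is available on major outcome events, including serious adverse events thought to be caused by treatment.

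**The concern.** The text describes a data set that the forms do not produce. A patient who survives a recurrent stroke, a myocardial infarction or a major bleed during the admission has no box on any form.

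Two things depend on those events. First, the monitoring committee is asked to weigh serious morbidity, and non-fatal strokes and major bleeds are serious morbidity. Second, detected DVT leads to anticoagulation, and the trial tests whether stockings change how often DVT is detected. Anticoagulant use may therefore differ between arms. The forms record that exposure and the reason for it, but not its best-known harm. If the trial runs on these forms, an effect of allocation on such events, in either direction, could not be reliably reported.

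**Working it through.** The plan gives no figure to reproduce and no arithmetic applies. The check sets the promised content against each form in the appendices.

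**Promised (Discharge Form section):** clinical DVT or PE; further vascular events during admission; complications of treatments.

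**What each outcome form asks:**

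| Form | Structured event items | Non-fatal vascular event other than DVT/PE | Bleeding |
|---|---|---|---|
| Discharge Form (Appendix 7), Major Events block | symptomatic DVT, PE, skin break | none | none |
| GP Questionnaire (Appendix 8) | DVT, PE, post-DVT leg syndrome, cause of death | none | none |
| Six-month patient form (Appendix 9) | leg clot, leg swelling, leg ulcer, lung clot | none | none |
| Six-month in-hospital form (Appendix 10), Major Events block | symptomatic DVT, PE, skin break, post-DVT leg syndrome | none | none |

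The Randomisation Forms hold baseline data and the Radiology Report Form holds scan findings, so neither fills the gap.

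**Where such events could still surface:**

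1. Cause of death on the Discharge Form has boxes for recurrent stroke, coronary heart disease and other vascular causes. These apply only to patients who died.
2. The Discharge Form ends with an open box for additional information. It does not ask about bleeds or vascular events, so an empty box does not mean that no event occurred. Entries would depend on who completes the form, and a comparison by arm cannot rest on that.
3. The drug questions record heparin or warfarin and the reason, with DVT or PE as one option. This captures exposure and not its complications.

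**Could the gap come from the PDF text?** The drug section of the Discharge Form is damaged in the text available. Its Major Events block is legible, and the parallel block of the in-hospital form has the same three items plus one. An item lost in conversion is therefore unlikely.

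**Result.** On the four outcome forms there are no structured items for non-fatal vascular events other than DVT and PE, and none for bleeding. The first conflicts directly with the Discharge Form section. The second conflicts with it only if complications of treatments is read to include anticoagulants.

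**The case against.** The strongest reply is that bleeding is never promised by name. Complications of treatments can be read as complications of the allocated stockings, which fits the secondary outcome on stocking complications, the skin-break item and the cause-of-death box for stockings. On that reading, a missing bleeding item is a design choice. This stands in part: the plural leaves the meaning open, so the bleeding limb is weaker than the vascular-event limb. The reply does not touch the vascular-event limb.

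A second reply is that net harm is not ignored. Death at 30 days and six months, the modified Rankin score and EuroQol are all outcomes analysed by intention to treat, and the committee may receive serious adverse events and request further analyses. That is also fair. But six-month disability does not identify the event behind it. Adverse events believed to be due to treatment depend on someone's attribution, and the protocol's list of ten appendices includes no adverse event form.

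A reader might infer three stronger things that the documents do not support:

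- *That no form records these events at all.* Fatal ones are ticked as causes of death, PE is dated, and free text is possible.
- *That the protocol itself says heparin does net harm in the patients its screening picks out.* The background statement concerns low dose heparin after acute ischaemic stroke. It does not address treatment of an accepted DVT.
- *That the number of patients put on heparin by screening, and the share of them falsely positive, can be calculated.* The 8% start-up rate is for the primary outcome, which also counts symptomatic DVT, and those patients would be investigated and treated under local protocols anyway. The stated sensitivity and specificity, applied as for one scan, do not carry over to an outcome built from two. No such count is relied on here.

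**Conclusion.** The concern holds in a limited form. The Discharge Form section and the forms contradict each other on non-fatal vascular events. Bleeding is also missing, although it is promised only indirectly. The consequence is that these non-fatal events cannot be compared by arm or reliably passed to the data monitoring committee.

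The size can be given only as missing items: none of the four outcome forms has one for either category. The documents give no rate for these events, so the number missed and any difference between arms are unknown and may be small. The primary outcome and its analysis are unaffected.

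The conclusion assumes that the appended forms are those in use and that no separate adverse event form exists outside the protocol. It should be corrected because the protocol claims the data and collecting them costs little.

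**What to change.** Add dated tick boxes to the Major Events block of the Discharge Form and of the in-hospital six-month form for:

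- recurrent stroke (ischaemic, haemorrhagic or unknown);
- myocardial infarction or other vascular event;
- major intracranial or extracranial bleed, with a short definition of major.

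List these as in-hospital safety outcomes under Secondary Outcomes, and report them by randomised arm, both there and to the data monitoring committee. The comparison should cover all randomised patients. Patients anticoagulated for a DVT are selected after randomisation, so bleeding in that group alone is not a randomised comparison and should not be the main one.

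The lesser alternative is to correct the Discharge Form section so that it describes only what the form asks. That removes the contradiction but leaves the committee without the data.

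The cost is a form reissue during recruitment, some extra data entry and a note check for patients already discharged, whose events will be recovered incompletely. Nothing in the management of DVT needs to change for this.

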#### **GP** Questionnaire

A questionnaire will be sent at 5½ months after randomisation to the GP of all patients who survive to discharge from hospital. This will establish that the patient is alive prior to sending out a follow-up form and ascertain whether they have had any DVT or PE since discharge.

#### Six Month Follow up Form

For those patients who have been discharged, outcome is assessed via a postal or telephone questionnaire. This will be sent to the patient directly from the CLOTS Co-ordinating Centre (for UK patients) or National Co-ordinating Centre (for non UK patients) after the patient's general practitioner has been contacted by post or phone to establish:

- that the patient is alive or the date and cause of death (if applicable)
- current address (to allow follow-up)

The six month questionnaire aims to establish:

- the place of residence (own home, with relatives, residential care or nursing home) [as a guide to resource use]
- their functional status degree of functional impairment on the Modified Rankin Scale (Bamford 1989), Simple Questions (Dennis et al 1997) and Health Related Quality of Life (HRQoL) measured using EUROQoL (EUROQol Group 1990)
- The current antithrombotic medication regimen
- Presence of symptoms which might reflect **post** DVT syndrome (e.g. leg swelling, ulcers)

If the patient is still in hospital when the six month follow-up is due, the randomising clinician / nurse will be sent a six month "in hospital" follow-up form which should be completed with the patient.

Patients' or relatives' approval will be routinely sought for information from the follow up to be fed back to the general practitioner. This will hopefully facilitate more effective management of patient's residual functional and emotional problems and any pain or discomfort being suffered.

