#### Secondary Outcomes

*In hospital:* symptomatic or asymptomatic DVT in the popliteal or femoral veins detected on either a Doppler ultrasound scan or contrast venography within 30 days of randomisation; death within 30 days, symptomatic or asymptomatic below knee DVT, confirmed fatal or non-fatal PE, medical complications of GCS (e.g. skin necrosis) and compliance with allocated treatment.

At six months: death from any cause, place of residence, post discharge DVT, PE, post DVT syndrome, disability (modified Rankin), and health related quality of life (EuroQol). The later effects of DVT/PE (e.g. breathlessness, leg pain or swelling, poor stroke recovery) or the complications of GCS (skin ulceration, amputation, loss of mobility) may be diverse, so it seems sensible to include a measure of overall health related quality of life.

Symptomatic DVTs, which occurred within 30 days of randomisation, would be counted in the primary endpoint. However, because the detection of such symptomatic DVTs is not blinded and hence prone to ascertainment bias, an analysis excluding these symptomatic DVTs will also be performed. Inevitably, some patients will not survive to have both routine Doppler ultrasounds and many of these will not have a detailed autopsy to establish whether they had a DVT or PE prior to death. However, it is possible that there will be an imbalance in the number of such deaths between the treatment groups especially if GCS are very effective in preventing fatal PE. Therefore, we will also perform an analysis combining our primary outcome

with death within 30 days, that is of 'death or confirmed symptomatic or asymptomatic DVT on routine Doppler ultrasound or contrast venography by Day 30'.

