#### ADDITIONAL INFORMATION

(Please use this space below for any additional information you may think relevant to the trial or to the patients treatment)

		Eor office use
		For onice use
Form completed by:	Date:	
ronn completed by.	Date:	
	Now please return this form by post to	
	new please retain the form by post to	
	The CLOTE Trial Co. ordinating Control	
	The CLOTS That Co-ordinaling Centre	
	[name],	
	Western General Hospital,	
	[name]	
	[name]	
	or hu	
	OF Dy	
	FAX on [name]	
	Thank you!	
	mank you:	

GP Questionnaire	
Patients Name: < <patient name="">></patient>	
Date of Birth: << Date of Birth >>	
Is this patient alive?  Yes  No If Yes please confirm the necessary	nat the following contact details are correct and amend if
address << address >>	
< <tel no.="">></tel>	
If the patient is dead or alive please tell us -	
Has the patient had any of the following sin	ce hospital discharge on < <date discharge="" of="">>?</date>
Deep Vein Thrombosis?	Yes No C II If yes give date first diagnosed ///
Pulmonary Embolism?	Yes No C
Evidence of post-DVT leg syndrome? (i.e. swelling, pain, new ulcer)	Yes No
If possible, please tell us how any of these diagn	oses were confirmed (e.g. venography,VQ scan)
If this patient has died, please confirm the date	of death / / (dd/mm/yyyy)
Cause of death:	0
Was cause of death confirmed by autopsy?	Yes 🗌 No 🗌
Completed by	Date /
Thank you very r	nuch for your assistance.
Now please fax us this form to	us at +[contact] or send to:
The CLOTS Trial Co-ordinating Centre, B [name], E	[name], Western General Hospital, dinburgh UK [name]

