#### CLOTS/FUP/V2

#### **PROBLEM WITH YOUR LEGS?**

Since discharge from hospital have you had a clot (DVT) in your legs? Yes					
If Yes, which leg is affected?					
My right leg	My left leg	Both legs			
Do you suffer from s	wollen ankles or legs?		Yes 🗌	No 🗌	
If Yes, which leg is a	ffected?				
My right leg 🗌	My left leg	Both legs			
Have you had a leg ulcer since your stroke? Yes No					
If Yes, which leg is affected?					
My right leg	My left leg	Both legs			
Since discharge from hospital, have you had a clot in your lungs ( PE) ? Yes 🗌 No 🗌					

In the next section we would like you to read the following descriptions from people who have similar medical problems to you and choose the one which best describes your present state.

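### The six-month ulcer questions reach back into the stocking-wearing period, so ulcers caused by stockings could be misclassified as post-DVT syndrome

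*Protocol*

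**What the plan says.** Protocol, Six Month Follow up Form, lists among the aims of the questionnaire: "Presence of symptoms which might reflect" post "DVT syndrome (e.g. leg swelling, ulcers"). Protocol, Secondary Outcomes, includes the syndrome in the six-month list: "place of residence, post discharge DVT, PE, post DVT syndrome, disability (modified Rankin"). The same paragraph refers to "the complications of GCS (skin ulceration, amputation, loss of mobility").

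The forms then ask about the outcome in different ways:

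- Patient questionnaire (Appendix 9): "Have you had a leg ulcer since your stroke", followed by which leg. Its thrombosis question is "Since discharge from hospital have you had a clot (DVT) in your legs", and the PE question has the same starting point.
- GP questionnaire (Appendix 8): evidence of post-DVT leg syndrome since hospital discharge, glossed as "i.e. swelling, pain, new ulcer".
- In-hospital six-month form (Appendix 10): the same gloss, under a stem that starts at randomisation. A later block, for patients in whom the syndrome has been diagnosed, asks about a leg ulcer since the stroke.

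The Discharge Form (Appendix 7) and the in-hospital form each have a separate, dated item for a skin break on either leg.

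**The concern.** Ulceration is both a sign of the late consequence of DVT and a named harm of the treatment. That overlap would be manageable if the forms could tell the two apart. The patient form cannot: its ulcer item spans the weeks when stockings were worn and asks for neither date nor cause.

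In Trial 1 the control group is to avoid GCS unless a clear indication arises, so ulcers caused by stockings would fall almost wholly in the stocking group. Any that were counted as post-DVT syndrome would add events to one arm only. A real reduction in the syndrome could be diluted, hidden or reversed, and a null effect could look like harm. The information needed to separate the causes has to be collected on the form, so an analysis plan written later could repair this only in part.

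**Working it through.** No figure in the protocol is at issue, so the check is a comparison of time windows, followed by an illustration of direction and possible size.

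**1. Stocking exposure.** Under Trial 1 and Trial 2, stockings go on as soon as possible after randomisation. They stay on until the patient is independently mobile, is discharged or declines them. Exposure therefore lies between randomisation and discharge.

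**2. Windows on the forms.**

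| Form | Item | Window starts at | Date asked | Leg side asked | Covers stocking wear |
|---|---|---|---|---|---|
| Patient (App. 9) | Leg ulcer | Stroke | No | Yes | Yes |
| Patient (App. 9) | DVT | Discharge | No | Yes | No |
| Patient (App. 9) | PE | Discharge | No | n/a | No |
| GP (App. 8) | Post-DVT syndrome | Discharge | Unclear in the text as read | No | No |
| In-hospital (App. 10) | Post-DVT syndrome | Randomisation | Date of first diagnosis | No | Yes |
| In-hospital (App. 10) | Ulcer detail | Stroke | No | Yes | Yes |
| Discharge and in-hospital (App. 7, 10) | Skin break | Randomisation | Yes | No | Yes |

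The information on post-DVT syndrome thus has three starting points: stroke, randomisation and discharge. Two of them take in the whole wearing period.

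**3. Can the existing items separate the causes?** Only partly. The skin-break item gives a date but no side. The patient's ulcer item gives a side but no date. The two cannot be matched by leg or by time.

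**4. Illustration for Trial 1 (all rates assumed).** Let c be the true syndrome rate without stockings, t the true rate with stockings, and s the rate of stocking ulcers counted as syndrome. Assume that every such ulcer is counted, that none occurs in controls, and that the two causes are independent. Then:

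observed stocking-arm rate = 1 − (1 − t)(1 − s)

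observed risk ratio = that rate ÷ c

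Example: c = 5%, t = 3%, s = 5% gives 1 − 0.97 × 0.95 = 7.85%, and 7.85 ÷ 5 = 1.57.

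| c | True risk ratio | s = 1% | s = 3% | s = 5% |
|---|---|---|---|---|
| 5% | 0.60 | 0.79 | 1.18 | 1.57 |
| 10% | 0.60 | 0.69 | 0.88 | 1.07 |
| 20% | 0.60 | 0.64 | 0.73 | 0.82 |
| 5% | 1.00 | 1.19 | 1.57 | 1.95 |
| 10% | 1.00 | 1.09 | 1.27 | 1.45 |
| 20% | 1.00 | 1.04 | 1.12 | 1.20 |

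A true ratio of 0.60 would read as exactly 1.00 when s = (c − t) ÷ (1 − t):

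- c = 5%: 0.02 ÷ 0.97 = 2.1%
- c = 10%: 0.04 ÷ 0.94 = 4.3%
- c = 20%: 0.08 ÷ 0.88 = 9.1%

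The direction is always against stockings. The size depends on rates that the protocol does not give.

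**5. Trial 2.** Both arms wear stockings. Any bias equals the difference in ulcer risk between the two lengths, and its direction cannot be derived from the protocol.

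**The case against.** The strongest reply is that the protocol only collects these symptoms as possible indicators and states no rule by which a reported ulcer becomes a case. Such a rule may sit in an analysis plan that is not shown. A reader might infer that an ulcer alone scores as post-DVT syndrome. The gloss on the GP and in-hospital forms, which names a new ulcer and no prior DVT, tempts one to that reading. But those items are completed by clinicians, who can exercise judgement, and on the in-hospital form the ulcer question from the stroke onward follows a diagnosis. The stronger reading is not supported.

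A reader might also infer that stocking injury is scored as thrombosis. It is not. The primary outcome rests on Doppler ultrasound or venography, DVT and PE have their own items, and the syndrome is listed apart from both.

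Three further points for the protocol are fair. The GP form starts at discharge, when stocking wear should be over. Skin breaks are recorded separately, and medical complications of GCS are a secondary outcome in their own right. The sentence naming skin ulceration is there to justify a quality-of-life measure; it is not a scoring definition. The protocol also calls the risks of GCS small and excludes patients in whom staff fear tissue necrosis, so s may be low. Trial 1 controls may wear stockings for a clear indication, which would dilute the contrast.

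None of this removes the narrower point. The patient form's ulcer window covers stocking wear and its answer carries no date or cause. An unseen analysis plan cannot recover what the form does not ask.

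**Conclusion.** The point holds as a weakness in how one secondary outcome is collected. Stocking ulcers could be misclassified as post-DVT syndrome, through the patient form and, for those still in hospital at six months, the in-hospital form. In Trial 1 the bias would run against stockings. In Trial 2 it depends on whether ulcer risk differs by stocking length.

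The size is unknown. The range of 0.64 to 1.57 for a true risk ratio of 0.60 rests on assumed syndrome rates of 5% to 20% and stocking-ulcer rates of 1% to 5%, with every such ulcer counted. A reader might infer from it that a benefit would in fact be cancelled. The protocol gives no rates that would support that conclusion. The primary outcome and the sample sizes are untouched. This is a minor but inexpensive improvement.

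**What to change.** - **Patient form:** split the ulcer question into during the hospital stay and since discharge, or ask for the date, and keep the leg side.
- **In-hospital six-month form:** ask for the date of any ulcer, since a split at discharge does not suit patients still in hospital. The form already records when stockings were last worn, so the two dates can be compared.
- **Skin-break item (Discharge Form and in-hospital form):** add leg side, so that a later ulcer can be matched to an earlier break.
- **Definition:** count only ulcers that arose after stocking wear ended towards post-DVT syndrome. Report in-hospital ulcers and skin breaks as GCS complications.
- **Sensitivity analysis only:** show a version restricted to patients with a recorded DVT. It should not be the main definition. The protocol assumes 70% sensitivity for Doppler and lets the second scan be waived before randomisation, so the restriction would drop syndrome that follows a missed DVT.

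The cost is slightly longer forms, one added definition and fewer syndrome events, some of which may be genuine.
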